	
to assess attainment of steady state.
 
To estimate the extent of accumulation after repeat dosing, the observed accumulation ratio for AUC (<math>(\text{RAUC}_{(0-\text{tau})})</math>), <math>C_{\max}</math> (<math>\text{RC}_{\max}</math>) and <math>C_{\text{tau}}</math> (<math>\text{RC}_{\text{tau}}</math>) may be determined.
 
Statistical analyses of the pharmacokinetic parameter data will be the responsibility of Biostatistics, GlaxoSmithKline. No formal hypotheses will be tested. Pharmacokinetic data will be presented in graphical and/or tabular form and will be summarized descriptively. Full details on the statistical aspects will be detailed in the Reporting and Analysis Plan (RAP).
 
Food Effect (SAD part)
 
The effect of food on the pharmacokinetics of GSK3186899 will be examined. <math>AUC(0-t)</math>, <math>AUC(0-\infty)</math> and <math>C_{\max}</math> of GSK3186899 will be analyzed after a <math>\log_e</math>-transformation of the data. An analysis of variance model will be fitted along with 90% confidence intervals using a mixed effects model, with fed/fasted condition as a fixed effect and subject as a random effect. Point estimates and corresponding 90% confidence intervals will be constructed for the comparisons of interest of GSK3186899 fed – GSK3186899 fasted, using the residual variance. These will then be back-transformed to provide point estimates and corresponding 90% confidence intervals for the geometric mean ratios fed: fasted.
 
Dose Proportionality (SAD and MAD parts)
 
Dose proportionality will be assessed following single doses of GSK3186899 (SAD part) via analyses of <math>AUC(0-\infty)</math> and <math>C_{\max}</math>.
 
Dose proportionality following repeated dosing (MAD part) will be assessed using <math>AUC(0-\text{tau})</math>, <math>C_{\max}</math> and <math>C_{\text{tau}}</math>.
 
A statistical analysis will be performed using the power model. The analysis will be performed on <math>\log_e</math>-transformed data. For each of these parameters a mixed effects model will be fitted with <math>\log_e</math> (dose) as a fixed effect and individual subject fitted as random effects. Estimates of the mean slopes of <math>\log_e</math> (dose) will be reported along with corresponding 90% confidence intervals (slope <math>\approx 1</math> implies dose proportionality).
 
Accumulation (MAD part)
 
The extent of accumulation of GSK3186899 will be based on AUC (<math>\text{RAUC}_{(0-\text{tau})}</math>), <math>C_{\max}</math> (<math>\text{RC}_{\max}</math>) and <math>C_{\text{tau}}</math> (<math>\text{RC}_{\text{tau}}</math>).
 
The focus of the statistical analysis will be to estimate the accumulation ratio, <math>R_o</math>, on the pharmacokinetics of GSK3186899. Following <math>\log_e</math>-transformation, <math>AUC(0-\text{tau})</math> on Day 1 and <math>AUC(0-\text{tau})</math> on the day of last dose will be analysed by a mixed

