
 To collect bile sample for analysis of metabolites of GSK3186899 (Part A fed regimen only) 	
 Metabolites of GSK3186899 in bile. These analyses will be detailed in a separate analysis plan.

* Accumulation ratios calculated as the ratio of last dose to first dose PK parameters: RAUC(0-tau) = AUC(0-tau) on last dose to AUC(0-tau) on first dose, RCmax = Cmax on last dose to Cmax on first dose, RCtau = Ctau on last dose to Ctau on first dose. # ARpred = 1/(1-e^(k*tau)) where k is elimination rate constant following the single dose and tau is the dosing interval for the intended repeat dosing.

† It is AUC(0-12) if dosing is BID, or, AUC(0-8) if dosing is TID.

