2.3. Study Design

Overview of Study Design and Key Features		
Figure 1 Study Design (Part A)		
Screening Period (28 days prior to D1)	Treatment Period	Follow-up Period (7-14 days post last dose)
Cohort 1 N = 8 (6A:2P)	DL1 → DL2 → DL3 → DL4 → 	
Cohort 2 N = 8 (6A:2P)	DL4 → DL5 → DL6 → DL7 → 	
Cohort 3 N = 14 (14A)	DLX →  DLX-FD → 	

All doses are fasted unless otherwise specified
 
♦ = Dose escalation meeting ◆ = Safety data review meeting
		
DL = Dose level; DLX = Dose level to be determined; FD = Fed Conditions; A = Active; P = Placebo		
Figure 2 Study Design (Part B)		
Screening Period (28 days prior to D1)	Treatment Period	Follow-up Period (7-14 days post last dose)
Cohort 4 N = 8 (6A:2P)	Repeat DL1 10 days → 	
Cohort 5 N = 8 (6A:2P)	Repeat DL2 10 days → 	
Cohort 6 N = 8 (6A:2P)	Repeat DL3 10 days → 	

♦ = Dose escalation meeting
 
DL = Dose level; A = Active; P = Placebo
 
Note: DL7 was not dosed in the study due to higher than expected exposures.
		
Design Features	
This study will be a randomized, double-blind (sponsor unblinded), placebo-controlled, 2-part study of the oral administration of GSK3186899A in healthy participants.
 
Planned to include approximately 54 participants and will consist of 2 parts as below:
 
 Part A will include a single-ascending, sequential crossover design in up to 3 cohorts of participants (Cohorts 1, 2 and 3). Part A Cohorts 1-2 will comprise of a 4 period crossover which includes 4 dosing regimens under fasted conditions. Part A Cohort 3 will comprise of a 2 period crossover which includes 1 dosing regimen 	

Overview of Study Design and Key Features	
	
under fasted conditions and 1 regimen under fed conditions. The fed conditions regimen will investigate the safety, tolerability and PK of a single dose of GSK3186899 following food administration.
 
 Part B will be a twice-daily (BID) 10-day repeat dose design in up to 3 parallel cohorts of participants (Cohorts 4, 5 and 6). Part B may include drug administration after either fed or fasted conditions, this will be dependent on the interim results from Part A. If under fasted conditions, participants will be required to fast at least 2 hours before and after drug administration.

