8.2.5.1. Statistical Methodology Specification

The following statistical analyses will only be performed if sufficient data is available (i.e. if subjects have well defined plasma profiles).

Pharmacokinetic analysis will be the responsibility of the Clinical Pharmacology Modelling and Simulation Department, (CPMS) and Statistical analyses of the pharmacokinetic parameters will be the responsibility of the Biostatistics Department.

(1) Statistical analysis for comparison of food effect – Single dose study part	
Endpoint / Variables	
 • AUC (0-t) • AUC(0-∞) • Cmax
Model Specification	
 • Log_e-transformed data will be statistically analysed using a Mixed model. • The mixed model will contain 
 ○ Fixed effect: fed or fasted status, period and their interaction term (if tested as significant) ○ Random effect: subject • Only data of subjects participating in Cohort 3 will be included in this analysis, all other dose level data from Cohorts 1 and 2 will be excluded from this analysis. • The Kenward and Roger method for approximating the denominator degrees of freedom and correcting for bias in the estimated variance-covariance of the fixed effects will be used. • An unstructured type of the covariance matrices R (accounting for the within subject variability) and G (accounting for the between subject variability) will be used. • Based on the intercurrent events observed in the study, appropriate strategies from Table 3 in Section 8.2.4 will be considered for handling of missing data (if any) and interpretation of food effect analysis results. If multiple intercurrent events are observed (for e.g., if the

subject does not take the full treatment as well he withdraws study consent), then the data will be handled using more than one strategy as described in Table 3 and interpretations of the results will be made accordingly.
Model Checking & Diagnostics

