
For the Mixed model, model assumptions will be checked, and appropriate adjustments may be applied based on the data.Distributional assumptions underlying the model used for analysis will be examined by obtaining a normal probability plot of the residuals and a plot of the residuals versus the fitted values (i.e. checking the normality assumption and constant variance assumption of the model respectively) to gain confidence that the model assumptions are reasonable.If there are any departures from the distributional assumptions, alternative transformations, such as data squared or square root of data, will be explored.Non-parametric analyses will be conducted if the normality assumption does not hold for any of the alternative transformations.If this model fails to converge, alternative covariance structures may be considered in the following order (1) Compound Symmetry (CS) and (2) Variance Components (VC).
Model Results Presentation

Point estimates and corresponding 90% confidence intervals will be constructed for the comparisons of interest of GSK3186899 fed – GSK3186899 fasted, based on the log-transformed data.These loge-transformed results will then be exponentially back-transformed to provide point estimates and corresponding 90% confidence intervals for the geometric mean ratios (GSK3186899 fed: GSK3186899 fasted).

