8.4.5.1. Statistical Methodology Specification

The following statistical analyses will only be performed if sufficient data is available (i.e. if subjects have well defined plasma profiles).

Pharmacokinetic analysis will be the responsibility of the Clinical Pharmacology Modelling and Simulation Department, (CPMS) and Statistical analyses of the pharmacokinetic parameters will be the responsibility of the Biostatistics Department.

Statistical analysis for dose accumulation – Repeat dose study part	
Endpoint / Variables	

 • RAUC(0-tau) • RCmax • RCtau 	
Model Specification	

 • Will be statistically analysed using a mixed model (MM) using a \log_e-transformation. The mixed model will contain: 
 ○ Fixed effects: dose, day and dose*day ○ Random effect: Subject 	

Here dose denotes the total dose administered per day to a subject.
 
 • The Kenward and Roger method for approximating the denominator degrees of freedom and correcting for bias in the estimated variance-covariance of the fixed effects will be used. • An unstructured type of the covariance matrices R (accounting for the within subject variability) and G (accounting for the between subject variability) will be used. • Based on the intercurrent events observed in the study, appropriate strategies from Table 5 in Section 8.4.4 will be considered for handling of missing data (if any) and interpretation of the analysis results. If multiple intercurrent events are observed (for e.g., if the subject does 	

not take the full treatment as well he withdraws study consent), then the data will be handled using more than one strategy as described in Table 5 and interpretations of the results will be made accordingly.

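### The food-effect and accumulation models pair an unstructured R with a random subject effect on two records per participant, so the R/G split is not identifiable (wrong as written; minor)

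*SAP*

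**What the plan says.** **Food effect (SAP 8.2.5.1).** The random part is "Random effect: subject". The covariance statement is "An unstructured type of the covariance matrices R (accounting for the within subject variability) and G (accounting for the between subject variability) will be used". Inference uses "The Kenward and Roger method for approximating the denominator degrees of freedom", with the matching small-sample variance correction. If the model does not converge, "alternative covariance structures may be considered in the following order (1) Compound Symmetry (CS) and (2) Variance Components (VC".

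**Accumulation (SAP 8.4.5.1).** The random part is "Random effect: Subject". The sentence on R and G, the Kenward-Roger method and the fallback order are the same as for the food effect.

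**Mock shells (SAP Appendix 13).** The footnotes of PK_T1 and PK_T4 repeat that both within- and between-subject covariances are unstructured, so this is not a stray sentence.

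**Records per participant.** SAP 2.3: "Part A Cohort 3 will comprise of a 2 period crossover which includes 1 dosing regimen" under fasted conditions and one under fed conditions. SAP 2.2: "Accumulation ratios calculated as the ratio of last dose to first dose PK parameters". Each model therefore has two records per participant for each parameter.

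**Protocol 10.5.2.** The food-effect model has fed/fasted condition as a fixed effect and subject as a random effect, and its confidence intervals are built "using the residual variance".

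**The concern.** Two records have a 2×2 marginal covariance with three distinct elements. An unstructured R already uses all three, so a random subject variance on top is redundant and the likelihood has no unique maximum in the covariance parameters. Kenward-Roger uses the inverse of the information matrix for those parameters, and that matrix is singular here.

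Three things follow:

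- The degrees of freedom and adjusted standard error behind the 90% intervals depend on how the software treats the singularity, which the SAP does not control.
- The fallback starts only on non-convergence. A routine that sets the subject variance to zero and reports convergence never reaches it. If it is reached, its first step has the same problem unless the random subject is dropped.
- An unstructured R supplies no single residual variance, which the protocol's food-effect interval calls for.

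**Working it through.** The plan states no figure for this point, so the check is a parameter count followed by numerical confirmation.

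**Inputs.** Two records per participant (SAP 2.2, 2.3). 12 evaluable participants and within-subject CV 20% for AUC (Protocol 10.2). Six active participants in each of three repeat-dose cohorts (SAP 2.3). Assumptions for illustration: between-subject CV 50%, two balanced sequences in Cohort 3.

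**Step 1: count.** Let g be the subject variance and V = R + g·11′.

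| Structure | Elements of V | Parameters | Rank |
|---|---|---|---|
| Unstructured R + random subject (specified) | r11+g, r12+g, r22+g | 4 | 3 |
| CS R + random subject (first fallback, random term kept) | s+c+g on the diagonal, c+g off it | 3 | 2 |
| σ²I + random subject (second fallback) | σ²+g on the diagonal, g off it | 2 | 2 |
| Unstructured R, no random subject | r11, r12, r22 | 3 | 3 |

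Reading G as a full 2×2 unstructured matrix makes it worse: six parameters, rank 3. A participant with only one period does not help, because one record informs only a diagonal element of V.

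**Step 2: what is and is not affected.** Within-subject variance is ln(1 + 0.20²) = 0.03922 and between-subject variance is ln(1 + 0.50²) = 0.22314. So V has 0.26236 on the diagonal and 0.22314 off it.

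- With g = 0: R has 0.26236 on the diagonal and 0.22314 off it.
- With g = 0.10: R has 0.16236 on the diagonal and 0.12314 off it.

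Both give the same V. The variance of the fed–fasted difference is (r11 + r22 − 2·r12)/12. It equals 2 × 0.03922/12 = 0.006537 in each case, so SE = 0.08085. The constant g cancels.

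**Step 3: likelihood.** On one simulated 12-participant crossover, −2REML was 5.00251111 at g = 0, 0.02, 0.04 and 0.06, with R adjusted and positive definite each time. Under CS it was 7.83417165 for every split of c and g tried. On a second simulated data set, g = 0, 0.02, 0.05 and 0.10 all gave −17.91721764, with contrast 0.0246 and SE 0.0783 throughout.

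**Step 4: Kenward-Roger when the singularity is handled.** The information matrix was inverted by pseudo-inverse, and then by dropping each of the four parameters in turn. For the food effect all five gave SE 0.08085 and df 10.0 (= 12 − 2), the same as unstructured R alone and as σ²I plus random subject. For accumulation all five gave SE 0.1143 (= √(2 × 0.03922/6)) and df 15.0 (= 18 − 3). With one-period dropouts in the 12-participant crossover, a generalised inverse again reproduced the unstructured-R-only results.

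**Step 5: Kenward-Roger when it is not handled.** An ordinary inverse of the singular matrix failed or gave arbitrary output. One run returned df 2.0 and SE 0.184 against df 10 and SE 0.079; other runs gave an undefined SE. Around a ratio of 1, that one run would give:

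- df 10: 1.812 × 0.079 = 0.143, so the 90% CI is 0.87 to 1.15.
- df 2: 2.920 × 0.184 = 0.537, so the 90% CI is 0.58 to 1.71.

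This shows what can happen, not what SAS (the software named in SAP Appendix 5) will do.

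**The case against.** The strongest defence is that the redundancy does no harm. V is identified, and the contrast and its unadjusted standard error depend only on V. Software that uses a generalised inverse, or sets the subject variance to zero, gives the analysis of unstructured R alone, which is itself a sound choice. The fallback text does not say which matrix CS replaces or whether the random term stays; with the random term dropped, CS is identifiable. The SAP also allows adjustments after model checking. All of this stands, and it keeps the point minor. What remains is that correct results depend on software behaviour the SAP leaves open.

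A reader might also infer more than the documents support:

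- **That the degrees of freedom are simply undefined.** Step 4 shows they are recovered when the singularity is handled.
- **That an unstable within-subject CV damages the results.** SAP 8.2.2 and 8.4.2 and shells PK_T1 and PK_T4 report estimates, ratios and 90% intervals from these models, not a within-subject CV.
- **That the structure would be chosen after unblinding.** Cohort 3 is open label and all active (Protocol 7.3.1, 7.3.2). Accumulation is a within-participant ratio on active doses. No formal hypotheses are tested (Protocol 10.1).

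**Conclusion.** Wrong as written, minor severity. The covariance specification in SAP 8.2.5.1 and 8.4.5.1 has one parameter too many for two records per participant. The first fallback has the same fault if the random subject is kept. Only the R/G split is unidentified; no bias in the food-effect or accumulation ratios is shown. The 90% intervals are those of unstructured R alone if the software handles the singularity, and can be arbitrary or missing if it takes an ordinary inverse.

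Separately, an unstructured R gives no single residual variance, so the SAP's food-effect interval does not match the protocol's description.

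The parameter count rests only on two records per participant. The numerical illustrations also assume 12 evaluable participants, balanced sequences and the CVs stated above. The time-invariance model (SAP 8.5.5.1) makes only G unstructured and is not part of this point.

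**What to change.** In SAP 8.2.5.1 and 8.4.5.1, specify one identifiable structure:

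1. **Random subject with R = σ²I.** This is the protocol's covariance structure. Keep the SAP's own additions: Kenward-Roger in both models and the period term in the food-effect model. Remove the CS/VC fallback.
2. **Unstructured R with no random subject.** Use CS R, also with no random subject, as the fallback. This option departs from the protocol's residual-variance wording, so record the change in SAP 2.1.

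Correct the footnotes of shells PK_T1 and PK_T4 to match. The cost is SAP wording only; no data, visits or sample size change.

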8.3.5.1. Statistical Methodology Specification

The following statistical analyses will only be performed if sufficient data is available (i.e. if subjects have well defined plasma profiles).

Pharmacokinetic analysis will be the responsibility of the Clinical Pharmacology Modelling and Simulation Department, (CPMS) and Statistical analyses of the pharmacokinetic parameters will be the responsibility of the Biostatistics Department.

(2) Statistical analysis for dose proportionality – Single and Repeat dose study parts	
Endpoint / Variables	

 For SAD part: AUC(0-∞), Cmax For MAD part: AUC(0-tau), Cmax, Ct_{tau} 	
Model Specification	

 Power model $y = \alpha * dose^\beta$ 
where y denotes the PK parameter being analyzed, dose denotes the total dose administered to a subject. The α denotes random subject effect in the repeat dose Part B. In the crossover single ascending dose Part A, alpha depends upon random subject effect and period effect.
 Log_e transformed data will be analysed by fitting the following terms in the mixed effect model: 
 Fixed effect: log_e (dose), period (period will be included in SAD part only) Random effect: Subject Data from all available doses in each part of the study will be considered (as described in Section 8.1.1.2). 	

• An unstructured covariance structure will be considered for the G matrix describing the between subject variability.• Based on the intercurrent events observed in the study, appropriate strategies from Table 4 in Section 8.3.4 will be considered for handling of missing data (if any) and interpretation of the analysis results. If multiple intercurrent events are observed (for e.g., if the subject does not take the full treatment as well he withdraws study consent), then the data will be handled using more than one strategy as described in Table 4 and interpretations of the results will be made accordingly.
Model Checking & Diagnostics

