
• For the Mixed Model, model assumptions will be checked, and appropriate adjustments may be applied based on the data.• Distributional assumptions underlying the model used for analysis will be examined by obtaining a normal probability plot of the residuals and a plot of the residuals versus the fitted values (i.e., checking the normality assumption and constant variance assumption of the model respectively) to gain confidence that the model assumptions are reasonable.• If there are any departures from the distributional assumptions, alternative transformations, such as data squared or square root of data, will be explored.• Non-parametric analyses will be conducted if the normality assumption does not hold for any of the alternative transformations.
Model Results Presentation

• Estimates of the mean slopes of $\log_e(\text{dose})$ will be reported along with corresponding 90% confidence intervals (slope ≈ 1 implied dose proportionality).

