8.4.2. Summary Measure

The summary measure will be the point estimates and 90% CIs of mean differences of 'Day 10 – Day 1' based on the log-transformed data and after back-transformation of this estimated differences, the geometric means of the ratio 'Day 10: Day 1' will be presented.

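### SAP 8.2 to 8.5: the squared and square-root fallback does not estimate the planned geometric mean ratio or log-log slope, and nothing is specified in its place

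*SAP*

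**What the plan says.** SAP 8.2 (food effect), 8.3 (dose proportionality), 8.4 (accumulation) and 8.5 (time invariance) each fit a mixed model to log_e-transformed PK parameters. The reported quantities follow from that scale:

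- **Food effect (8.2.5.1):** log differences are "exponentially back-transformed to provide point estimates and corresponding 90% confidence intervals for the geometric mean ratios".
- **Accumulation (8.4.2):** log differences between days are back-transformed to "the geometric means of the ratio" Day 10 to Day 1. Section 8.5.2 does the same for time invariance.
- **Dose proportionality (8.3.5.1):** log_e "transformed data will be analysed by fitting the following terms in the mixed effect model", with log_e(dose) as a fixed effect. The estimate is read as "slope ≈ 1 implied dose proportionality".

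The model-checking text is the same in all four: on any departure from the distributional assumptions, "alternative transformations, such as data squared or square root of data, will be explored". The next step is: "Non-parametric analyses will be conducted if the normality assumption does not hold for any of the alternative transformations". Departures are judged from a normal probability plot and a residual plot, and no threshold is given.

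Protocol 10.5.2 specifies log_e analysis for food effect, dose proportionality and accumulation, and has no squared, square-root or non-parametric step. SAP 2.1 declares one minor change (moving Ctau from the single-dose to the repeat-dose part) and does not mention this one.

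**The concern.** A ratio comes from exponentiating a difference of logs, and a proportionality slope of 1 comes from regressing log exposure on log dose. A difference of square roots or of squares is not a log ratio. A slope of root or squared exposure on log dose depends on the concentration units and has no reference value of 1.

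The order of steps matters. Non-parametric analysis is reached only when no alternative transformation looks normal, so an alternative that does look normal ends the search. On that sequence it stands in for the log model and is not a check on it. The SAP then has an analysis whose result its own results text and mock shells (PK_T1 to PK_T4) cannot present. Putting the number into the existing shell would give a wrong ratio, or a slope that cannot be compared with 1. The choice would also be made after seeing the data, on small samples: 10 to 12 evaluable participants in Cohort 3 and 6 active per Part B cohort.

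**Working it through.** **Planning figure.** Protocol 10.2 gives precision of 16% (AUC, CVw 20%) and 24% (Cmax, CVw 30%) for 12 evaluable participants.

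- σ_w = √ln(1+CVw²) = 0.198 and 0.294.
- h = t(0.95, 11) × σ_w × √(2/12), with t = 1.796, so h = 0.145 and 0.215.
- exp(h) − 1 = 15.6% and 24.0%.

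Both percentages reproduce, so the planned precision assumes the log scale. (The printed interval limits are wider than exp(±h). That is a separate matter and is not used here.)

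**Dose proportionality.** Inputs are the dose-independent AUC(0-24h) values in protocol Table 5: 0.82, 1.61, 3.23, 8.23, 16.59 and 32.77 ug.h/mL at 30, 60, 120, 300, 600 and 1200 mg. These are close to proportional. With x = ln(dose), mean x = 5.246 and Σ(x − x̄)² = 9.875. The least-squares slope is b = Σ(x − x̄)f(AUC) / 9.875.

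| f(AUC) | Σ(x − x̄)f(AUC) | slope |
|---|---|---|
| log_e, either unit | 9.916 | 1.00 |
| square root, ug.h/mL | 12.608 | 1.28 |
| square root, ng.h/mL | 398.69 | 40.4 |
| squared, ug.h/mL | 2319.6 | 235 |

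Moving from ug to ng adds ln(1000) to every log value and leaves the slope alone. It multiplies root values by √1000 = 31.6 and squared values by 10⁶.

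SAP 5.1 lists dose level 6 as 800 mg, so the fit was repeated on exactly proportional data at 30, 60, 120, 300, 600 and 800 mg, with AUC 0.82 at 30 mg. The log slope is 1.000. The root slope is 1.149 (ug) or 36.3 (ng), and the squared slope is 126 (ug).

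**Food effect.** Assume a true fed:fasted ratio of 0.80 and noise-free data, and apply the planned exponential back-transformation:

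- Square root, fasted AUC 8.23: √(0.80 × 8.23) − √8.23 = 2.566 − 2.869 = −0.303, and exp(−0.303) = 0.74.
- Square root, fasted AUC 16.59: 3.643 − 4.073 = −0.430, and exp(−0.430) = 0.65.
- Square root, first case in ng.h/mL: −0.303 × 31.62 = −9.58, and exp(−9.58) = 7 × 10⁻⁵.
- Squared, fasted AUC 8.23: 0.64 × 8.23² − 8.23² = −24.4, and exp(−24.4) = 2.6 × 10⁻¹¹.

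On the log scale the answer is 0.80 in every case. A true ratio of exactly 1 still gives 1, so the error is in the size of any effect. The same algebra applies to Day 10 against Day 1 in 8.4 and 8.5.

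**The case against.** - **The alternatives are only to be explored.** The results text in 8.2, 8.4 and 8.5 still refers to log-transformed data, 8.3 still reports the slope on log_e(dose), and no display is planned for another scale. This stands in part. A reader might infer that the SAP orders the log results to be replaced, and the documents do not go that far. They leave open what is reported after a departure, while the order of steps points towards substitution.
- **The ratio and the power-model slope exist whatever the scale.** This stands. A reader might infer that they are undefined off the log scale. In fact a ratio of back-transformed means can be formed, and the power model can be fitted without logging exposure. But with root (λ = 0.5) or squared (λ = 2) lognormal data, that ratio is GMR × exp[λ(σ²_fed − σ²_fasted)/2], which equals the geometric mean ratio only when the log-variances match. For a true 0.80, assumed CVs of 30% fasted and 50% fed give 0.83 (root) and 0.92 (squared). Reversing the CVs gives 0.77 and 0.70. The SAP specifies neither this quantity nor its interval.
- **The protocol defers statistical detail to the RAP.** True, and diagnostics belong there. A change of scale is more than detail when the protocol states log_e.
- **Little depends on it.** The analyses are secondary, no hypotheses are tested, and Biostatistics produces no displays for the dose-escalation meetings. A reader might infer that the fallback would steer the fed or fasted choice for Part B. The interim displays in SAP Table 1 instead list a fed-to-fasted ratio summary from CPMS, not the 8.2 model. This limits the severity.

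No probability of triggering the fallback can be given, because the check is visual and has no stated level.

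**Conclusion.** The concern holds in a limited form. In all four analyses an uncriterioned visual finding leads to scales on which the fitted model does not estimate the planned summary measure, and the SAP names no substitute measure, back-transformation or display. The protocol has no such step, and SAP 2.1 does not declare one.

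The slope result rests on projected exposures and shows that the number cannot be read against 1. It does not predict what the trial's data would give. The 0.74 and 0.65 rest on an assumed true ratio of 0.80 and on someone applying the only back-transformation the SAP provides. It cannot be concluded that the reported analysis will change, only that the SAP permits this and does not say what would then be reported. The primary safety objective is unaffected. Severity is low to moderate.

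**What to change.** In the model-checking text of SAP 8.2.5.1, 8.3.5.1, 8.4.5.1 and 8.5.5.1:

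1. Delete the squared and square-root options.
2. State that the log_e model is always the reported analysis, whatever the residual plots show.
3. Replace the open-ended non-parametric step with a named sensitivity analysis that keeps the estimand. For food effect, accumulation and time invariance, use a Hodges-Lehmann estimate with a rank-based 90% CI on within-subject log differences, exponentiated to a ratio. This is feasible with six active participants per Part B cohort: the exact signed-rank interval that cuts P(T ≤ 2) = 3/64 from each tail has coverage 1 − 6/64 = 90.6%. For dose proportionality, use a robust or rank-based log-log slope. Part B participants join one cohort only, so there is no within-subject dose contrast there.
4. Do not exclude outliers after seeing the residuals. That would be another data-dependent choice in a small sample.

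If the sponsor prefers to keep a further scale, the SAP should give its summary measure, interval method and display, and 2.1 should declare the change. The cost is SAP wording and a footnote in the mock shells, with no new data or design change.
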